#### 3.3.3.2.2 Infectious Disease Exclusion Criteria

11. Increased risk of infectious complications (e.g. due to past organ or stem cell transplantation)
12. Live or attenuated vaccination within 6 weeks prior to randomization
13. Patients with a positive QuantiFERON TB test during screening are excluded, unless:
  - Patient had previous diagnosis of active or latent TB and has completed appropriate treatment per local practice/guidelines within the last 3 years and at least 6 months before first administration of trial medication under this protocol (patients may be re-screened once to meet this criterion)
  - Patients with suspected false positive or indeterminate QuantiFERON TB result may be re-tested once
  - If Quantiferon not available or providing indeterminate results after repeat testing : A tuberculin skin test reaction  $\geq 10\text{mm}$  ( $\geq 5\text{mm}$  if receiving  $\geq 15\text{mg/d}$  prednisone or its equivalent)
14. Relevant chronic or acute infections including active tuberculosis, human immunodeficiency virus (HIV) infection or viral hepatitis. A patient can be re-screened if the patient was treated and is cured from the acute infection.

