### 5.2.3 Safety laboratory parameters

The safety laboratory samples will be taken for the *Screening Cohort* according to their local standard of care. No specific parameters are requested.

[Section 5.2.3](#) is applicable for the *Study Cohort*, only.

Safety laboratory parameters to be assessed are listed in [Table 5.2.3:1](#) and [5.2.3:2](#). For the sampling time points please see the [Flow Chart](#). More frequent blood sampling may be done whenever the investigator deems necessary. Unscheduled safety laboratory examinations will be reported in the CRF along with the results.

All safety laboratory analyses will be performed by a local laboratory.

It is preferred but the patients do not have to be fasted for the blood sampling for the safety laboratory.

It is the responsibility of the investigator to evaluate the laboratory results from the local laboratory.

Clinically relevant abnormal findings as judged by the investigator will be reported as baseline conditions or adverse events (please refer to [Section 5.2.6](#)).

A clinically relevant value may be either in- or outside the reference range. Clinically relevant abnormal laboratory test results must be confirmed and should be repeated until normalization or stabilization or until an alternative explanation has been found. Abnormal laboratory values will be also graded for intensity by using RCTC Version 2.0 criteria. ([R13-3515](#)).

In case the criteria for hepatic injury are fulfilled, a number of additional measures will be performed (please see [Section 5.2.6.1](#)) and the DILI Checklist provided in the ISF eDC system. The amount of blood taken from the patient concerned will be increased due to this additional sampling.

Table 5.2.3: 1 Exclusionary testing

Category	Test name
Infection testing	Hepatitis B Surface Antigen (qualitative)  Hepatitis B core Antibody  HBV-DNA (quantitative PCR)  Hepatitis C Antibodies (qualitative)  HIV-1, and HIV-2 Antibody (qualitative) 
TB screening	QuantiFERON®-TB 
Serum Pregnancy test (only for female patients of childbearing potential) 1)	Human Serum Chorionic Gonadotropin
Stool studies to evaluate for enteric pathogens 1)	Salmonella Shigella Yersinia Campylobacter E. coli Clostridia difficile toxin Enteric parasites and their ova (including Cryptosporidia)

 At screening only (visit 1)

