 A HBV-DNA should be conducted if Hepatitis B core Antibody is positive and Hepatitis B Surface Antigen is negative (definition of occult HBV infection: B core Antibody is positive, Hepatitis B Surface Antigen is negative; HBV DNA detectable).

 There is the trial site option to perform a PPD skin test

 If the 1st QuantiFERON®-TB test result is undetermined, a re-test should be performed. If the re-test QuantiFERON-TB test result is undetermined, a PPD skin test should be performed.

Table 5.2.3: 2 Laboratory tests

Category	Test name
Haematology	Haematocrit (Hct) Haemoglobin (Hb) Glycosylated Hbc (HbA1c) (only at screening) Red Blood Cell Count/ Erythrocytes Reticulocyte Count White Blood Cells / Leukocytes Platelet Count/ Thrombocytes
Diff. Automatic	Neutrophils (relative and absolute count) Eosinophils (relative and absolute count) Basophils (relative and absolute count) Monocytes (relative and absolute count) Lymphocytes (relative and absolute count)
Diff. Manual (if Diff Automatic is abnormal)	Neutrophils, bands (Stabs) Neutrophils, polymorphonuclear (PMN) Eosinophils Basophils Monocytes Lymphocytes
Coagulation	Activated Partial Thromboplastin Time (aPTT) Prothrombin time (INR) Fibrinogen
Enzymes	AST (GOT) ALT (GPT) Alkaline Phosphatase (AP) Creatine Kinase (CK) CK-MB, only if CK is elevated Gamma-Glutamyl Transferase (GGT/ $\gamma$ -GT) Lactic Dehydrogenase (LDH) Amylase Lipase
Electrolytes	Calcium Sodium Potassium Chloride
Substrates	Glucose BUN (blood urea nitrogen) Uric acid Creatinine eGFR (estimated by CKD-EPI formula) (only at screening) Bilirubin Total Bilirubin Direct (if total is elevated) Bilirubin Indirect (if total is elevated) Troponin (Reflex, in case of elevated CK) Protein, Total Albumin C-Reactive Protein (CRP) Cholesterol, total Triglycerides LDL-Cholesterol HDL-Cholesterol

Table 5.2.3: 2 Laboratory tests (cont.)

Category	Test name
Specific gamma-globulin quantification	IgE  , IgG
Urine Pregnancy test (only for female patients of childbearing potential)	Human Chorionic Gonadotropin in urine
Serum Pregnancy test (only for female patients of childbearing potential if urine pregnancy test is positive)	Human Serum Chorionic Gonadotropin
Hormones (only at screening)	TSH (free T3 and free T4 in case of abnormal TSH result)
Urinalysis (dipstick)	Urine Nitrite Urine Protein Urine Glucose Urine Ketone Urobilinogen Urine Bilirubin Urine RBC/ Erythrocytes Urine WBC/ Leukocytes Urine pH

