## **7.7 DETERMINATION OF SAMPLE SIZE**

It is planned to include a total of approximately 5-8 patients in the Screening Cohort and approximately 20 patients in the Study Cohort of this trial. The number of patients is not based on a power calculation but on feasibility, coordinating investigator's experience with regard to recruitment and practical considerations.

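### As written, exclusion criterion 13 does not exclude a patient with a positive tuberculin skin test, and no other text states what that result means for eligibility

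*Protocol*

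**What the plan says.** Criterion 13 in Protocol 3.3.3.2.2 opens: "Patients with a positive QuantiFERON TB test during screening are excluded, unless". Three items follow at the same list level:

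- a completed course of TB treatment within stated time limits;
- a re-test rule: "Patients with suspected false positive or indeterminate QuantiFERON TB result may be re-tested once";
- a skin-test item: "If Quantiferon not available or providing indeterminate results after repeat testing : A tuberculin skin test reaction" of at least 10 mm, or at least 5 mm for a patient on 15 mg/d or more of prednisone or equivalent.

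Protocol 5.2.3 places TB screening in Table 5.2.3:1, whose title is "Exclusionary testing". Footnote 3 says: "There is the trial site option to perform a PPD skin test". Footnote 4 covers a second inconclusive blood test: "If the re-test QuantiFERON-TB test result is undetermined, a PPD skin test should be performed". Neither footnote gives a cut-off or says what the result means for eligibility.

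Criterion 14, the next in the list, reads: "Relevant chronic or acute infections including active tuberculosis, human immunodeficiency virus (HIV) infection or viral hepatitis".

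**The concern.** The table title suggests that the skin test is there to keep patients out. The criterion that should give it that effect lists the positive result among the exceptions and attaches no consequence to it. A site that follows the literal text has no ground in criterion 13 to exclude a skin-test-positive patient. A site that follows the apparent intent excludes the same patient.

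Three features of the trial make this worth correcting:

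- Protocol 1.4 names exclusion of patients at increased infection risk as a mitigation measure, and 5.2.6.1 makes mycobacterium tuberculosis infection an adverse event of special interest.
- Protocol 4.2.1 permits background oral steroids up to 20 mg/d prednisone equivalent, thiopurines or methotrexate, and anti-TNF treatment. The 15 mg/d stratum of the skin-test item can therefore occur in this population.
- Protocol 3.3 plans about 20 patients at about 20 sites, roughly one per site. Nearly every eligibility decision is made by a different team. Under 8.3.1 each team must document that no exclusion criterion is met.

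**Working it through.** The plan has no figure to reproduce here. The sample size rests on feasibility (Protocol 7.7: "The number of patients is not based on a power calculation"), and no rate of unavailable or indeterminate QuantiFERON results is given. The check is a reading of the criterion against the rest of the protocol.

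**Step 1: apply criterion 13 literally to each screening result.**

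| QuantiFERON | Skin test | Lead sentence triggered? | Excluded by criterion 13? |
|---|---|---|---|
| Positive | – | Yes | Yes, subject to the exceptions |
| Negative | – | No | No |
| Unavailable, or indeterminate after re-test | Below cut-off | No | No |
| Unavailable, or indeterminate after re-test | At or above cut-off | No | No |

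The last two rows give the same answer. For the patients who are sent to a skin test, its result makes no difference under criterion 13.

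**Step 2: find why.** There are two separate faults.

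- *Trigger.* The lead sentence needs a positive QuantiFERON. The skin-test item concerns patients who do not have one.
- *Position.* The item sits in a list of exceptions to exclusion and contains no words that make the reaction exclusionary.

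Correcting only one leaves the other. A wider trigger would still leave the reaction listed as an exception. Moving the item without adding a consequence would still leave nothing operative.

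**Step 3: look for another sentence that closes the gap.**

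- Table 5.2.3:1, footnotes 3 and 4: a skin test is optional, or called for after a second undetermined result. No cut-off or consequence is stated. Footnote 3 is also wider than criterion 13, which mentions the skin test only when QuantiFERON is unavailable or repeatedly indeterminate.
- Criterion 11: raised risk of infectious complications in general terms, with transplantation as the example. TB and skin tests are not named.
- Criterion 14: names active TB as one example among relevant infections. Latent TB and skin tests are not named.
- Criterion 22: clinically significant conditions or findings, in the investigator's opinion. TB and skin tests are not named.

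Criteria 11, 14 and 22 could be used against a skin-test-positive patient, but only by judgement.

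**Step 4: size.** Let *q* be the share of randomised patients who reach the fallback test, *p* the share of those with a positive reaction, *s* the chance that the site applies the literal text, and *j* the chance that criterion 11, 14 or 22 is used anyway. The expected number dosed because of the wording is 20 × *q* × *p* × *s* × (1 − *j*).

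The documents give none of these. If *q* is assumed to be 2% to 10%, 20 × 0.02 = 0.4 and 20 × 0.10 = 2 patients reach the fallback. The other factors are each at most 1, so 0.4 to 2 is a ceiling under that assumption. It does not estimate how many patients would be exposed.

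**The case against.** The best reply is that the intent is plain. The list is visibly mixed: the re-test item is a procedural sentence and not a true exception, so the skin-test item can be read as a fallback exclusion finding that landed in the wrong list. Section 3.3.3.2 bars enrolment of anyone meeting an exclusion criterion, and the table title points the same way. List levels may also have been disturbed when the PDF was read. Most sites would probably exclude.

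Much of this stands, and it limits how far the point can go:

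- A reader might infer that the protocol exempts skin-test-positive patients or clears them for dosing. The text does not support that. A patient with no positive QuantiFERON is outside the lead sentence and so cannot be exempted from it. The item is incoherent as written; it is not a workable permission.
- A reader might infer that nothing in the protocol could keep such a patient out. Criteria 11, 14 and 22 could, by judgement, and the wording of criterion 14 is not confined to active TB.
- A reader might count every patient who reaches the fallback test as exposed. That skips the need for a positive reaction, a literal-minded site and no use of the judgement-based criteria. QuantiFERON is scheduled for every Study Cohort patient at Visit 1a (Flow Chart B), so the fallback should be the less common route.

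The reply does not cure the defect. At any list level, the item lacks words saying that the reaction excludes. A clear intent shows that the wording departs from it, and relying on sites to disregard the literal text is not a control.

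**Conclusion.** Wrong as written. Criterion 13 does not exclude a patient whose QuantiFERON is unavailable or indeterminate after repeat testing and whose skin test is at or above the stated cut-off. This contradicts the evident purpose of Table 5.2.3:1, where the skin test has no stated eligibility consequence either. What remains is investigator judgement under criteria 11, 14 and 22.

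The number of patients affected is likely to be small and cannot be estimated from the documents. The 2% to 10% used above is an assumption. The conclusion about the wording does not depend on it. The conclusion about intent rests on the table title and on the place of the test in the screening scheme. Endpoints and planned analyses are not affected. The reason to act is that a stated infection-risk safeguard has no operative wording, and correcting it is cheap.

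**What to change.** Reconcile criterion 13 with Table 5.2.3:1, footnotes 3 and 4. Move the skin-test item out of the exception list, and state in its own sentence what a skin-test result means for eligibility. Make the footnotes refer to that sentence.

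Three matters are for the sponsor to decide, and the corrected text should state each one: which skin tests the sentence covers (only the fallback in criterion 13 and footnote 4, or also the general site option in footnote 3), which cut-offs apply, and whether the completed-treatment exception extends to a skin-test result. The present text does not settle the first or the third, so a correction that silently assumed an answer would create a new eligibility rule.

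The cost is a one-sentence protocol correction and a clarification to sites. The correction itself calls for no new test and no change to the analysis plan.

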#### 3.3.3.2.3 General Exclusion Criteria

15. Any documented active or suspected malignancy or history of malignancy within 5 years prior to screening, except appropriately treated basal cell carcinoma of the skin, squamous cell carcinoma of the skin, or in situ carcinoma of uterine cervix.

16. Major surgery (major according to the investigator's assessment) performed within 12 weeks prior to randomization or planned during study conduct, e.g. hip replacement.
17. Pathological safety lab parameters: haemoglobin < 8 g/dL, total white blood count (WBC) < 3000 cells/ $\mu$ l, neutrophils < 1000 cells/ $\mu$ l, thrombocytes < 100.000/ $\mu$ l, creatinine  $\geq$  2 mg/dL, total bilirubin > 2 x ULN with ratio of direct/indirect >1 (patients with Gilbert's syndrome are not excluded), Alkaline Phosphatase >3 x ULN.
18. Patients who must or wish to continue the intake of restricted medications ([see section 4.2.2.1](#)) or any drug considered likely to interfere with the safe conduct of the trial
19. Previous enrolment in this trial (exception: patients of screening cohort may be enrolled in study cohort)
20. Currently enrolled in another investigational device or drug trial. Specific restrictions for patients who have participated recently in another drug trial are listed in [section 4.2.2](#)
21. Women who are pregnant, nursing, or who plan to become pregnant in the trial
22. Evidence of a current or previous disease, medical condition (including chronic alcohol or drug abuse) other than crohn's disease, surgical procedure, medical examination finding (including vital signs and electrocardiogram (ECG)), or laboratory value at the screening visit outside the reference range that in the opinion of the investigator is clinically significant and would make the study participant unreliable to adhere to the protocol or to complete the trial, compromise the safety of the patient, or compromise the quality of the data
23. History of allergy/hypersensitivity to the systemically administered trial medication agent or its excipients or to contrast media.

### 3.3.4 Withdrawal of patients from therapy or assessments

Patients may discontinue trial treatment (not applicable for Screening Cohort) or withdraw consent to trial participation as a whole ("withdrawal of consent") with very different implications; please see [sections 3.3.4.1](#) and [3.3.4.2](#) below.

Every effort should be made to keep the patients in the trial: if possible on treatment (not applicable for Screening Cohort), or at least to collect important trial data.

Measures to control the withdrawal rate include careful patient selection, appropriate explanation of the trial requirements and procedures prior to trial enrolment, as well as the explanation of the consequences of withdrawal.

The decision to discontinue trial treatment (not applicable for Screening Cohort) or withdraw consent to trial participation and the reason must be documented in the patient files and CRF. If the reason for discontinuation is death, this should be reported on the SAE form as well, regardless of causal relationship.

#### 3.3.4.1 Discontinuation of trial treatment

Not applicable for *Screening Cohort*. Applicable for *Study Cohort*, only.

An individual patient will discontinue trial treatment if:

- The patient wants to discontinue trial treatment, without the need to justify the decision.
- The investigator clinical judgement advises for it.

- The patient has repeatedly shown to be non-compliant with important trial procedures and, in the opinion of both, the investigator and sponsor representative, is not willing or able to adhere to the trial requirements in the future.
- The patient needs to take concomitant medication that interferes with the investigational medicinal product or other trial treatment. Please refer to the [section 4.2.2](#) for restricted medications.
- The patient needs surgical interventions for CD including any fistula surgical procedures (except seton drainage, see [section 4.2.2.2](#))
- The patient can no longer receive trial treatment for medical reasons (such as surgery, adverse events, other diseases, or pregnancy).
- For individual stopping rules related to specific adverse events, please see [section 4.2.1](#)

In case of a temporary reason, trial treatment should be restarted if medically justified, please see [section 4.1.4](#).

Even if the trial treatment is discontinued, the patient remains in the trial and, given his/her agreement, will undergo the procedures for early treatment discontinuation and follow up as outlined in the [Flow Chart B](#) and [C](#) and [section 6.2.2](#).

#### 3.3.4.2 Withdrawal of consent to trial participation

Patients may withdraw their consent for trial participation at any time without the need to justify the decision.

If a patient wants to withdraw consent, the investigator should be involved in the discussion with the patient and explain the difference between trial treatment discontinuation (not applicable for Screening Cohort) and withdrawal of consent to trial participation, as well as explain the options for continued follow up after trial treatment discontinuation, please see [section 3.3.4.1](#) above.

#### 3.3.4.3 Discontinuation of the trial by the sponsor

Boehringer Ingelheim reserves the right to discontinue the trial overall or at a particular trial site at any time for the following reasons:

1. Failure to meet expected enrolment goals overall or at a particular trial site.
2. Emergence of any efficacy/safety information invalidating the earlier positive benefit-risk-assessment that could significantly affect the continuation of the trial.
3. Violation of GCP, the trial protocol, or the contract impairing the appropriate conduct of the trial.

The investigator / the trial site will be reimbursed for reasonable expenses incurred in case of trial termination (except in case of the third reason).

## 4. TREATMENTS

### 4.1 INVESTIGATIONAL TREATMENTS

Patients in *Screening Cohort* will not be treated with trial medication. For this reason, the chapter 4.1 is not applicable for *Screening Cohort*.

#### 4.1.1 Identity of the Investigational Medicinal Products

Table 4.1.1: 1 Description of test product BI 655130 i.v.

Substance:	BI 655130
Pharmaceutical formulation:	Solution for infusion
Source:	Boehringer Ingelheim Pharma GmbH & Co. KG
Unit strength:	60mg/ml
Posology	Study Cohort: 1200mg every 4 week 

• Period 1: at week 0, 4, 8

• Period 2: at week 12, 16, 20

Route of administration:	Intravenous (i.v.)
Duration of use	24 weeks

Table 4.1.1: 2 Description of test product placebo matching to BI 655130 i.v.

Substance:	Placebo matching to BI 655130
Pharmaceutical formulation:	Solution for infusion
Source:	Boehringer Ingelheim Pharma GmbH & Co. KG
Unit strength:	Not applicable

Table 4.1.1: 2 Description of test product placebo matching to BI 655130 i.v. cont.

Posology	Study Cohort: 0 mg (placebo) every 4 week 

• Period 1: at week 0, 4, 8

• Period 2: at week 12, 16, 20

Route of administration:	Intravenous (i.v.)
Duration of use	24 weeks

#### 4.1.2 Selection of doses in the trial

The aim of this small exploratory study is to provide the highest likelihood to study the mechanism of BI 655130 in CD [REDACTED]

[REDACTED] Based on other effective anti-cytokine drugs in IBD and pre-clinical assays for IL-36 inhibition, a monotonic rather than a bell-shaped dose-response curve is expected. Thus, the highest tolerated dose (1200 mg i.v. q4w) should provide the highest likelihood to achieve this objective. This dose is also expected to provide the best chance to induce clinical remissions in CD patients. Whether lower doses will be sufficient to achieve maximum efficacy will be subject of subsequent studies. This dose regimen is the highest covered by current healthy volunteer PK and safety data for individuals.

Currently approved or investigational biologics (e.g. TNFi, vedolizumab, ustekinumab) have established 4-8 weeks duration of induction treatment in CD; a longer induction period of 12 weeks (patients on placebo in period 1) or 24 weeks (patients on BI 655130 in period 1) was selected to allow assessment of the response kinetics for BI 655130, which represents a new and clinically non-validated MoA.

The dosing interval of once every 4 weeks is supported by the long half-life of BI 655130.

#### 4.1.3 Method of assigning patients to treatment groups

##### Study Cohort, Period 1: Double blind

During visit 2 eligible patients in Study Cohort will be randomised to receive 12 weeks of treatment (i.e. three administrations) with BI 655130 1200mg i.v. every 4 weeks or matching placebo in a 1:1 ratio according to a randomization plan. The assignment will occur in a blinded fashion via Interactive Response Technology (IRT).

##### Study Cohort, Period 2: Double blind

Treatment in period 2 starting in visit 6 (BI 655130 1200mg i.v. every 4 weeks or placebo) will be determined by the outcome at week 12 (cf. [section 3.1](#)). The assignment will occur in a blinded fashion via Interactive Response Technology (IRT).

Details regarding the use of the IRT are described in the site-user manual available in the ISF.

